8.1.2 Serious Adverse Event Definition

Serious AE (SAE) means any untoward medical occurrence that at any dose:

1. Results in **death**.
2. Is **life-threatening** (refers to an AE in which the patient was at risk of death at the time of the event. It does not refer to an event which hypothetically might have caused death if it were more severe).
3. Requires inpatient **hospitalization or prolongation of an existing hospitalization** (see clarification in the paragraph below on planned hospitalizations).
4. Results in **persistent or significant disability or incapacity**. (Disability is defined as a substantial disruption of a person's ability to conduct normal life functions).
5. Is a **congenital anomaly/birth defect**.
6. Is a **medically important event**. This refers to an AE that may not result in death, be immediately life threatening, or require hospitalization, but may be considered serious when, based on appropriate medical judgment, may jeopardize the patient, require medical or surgical intervention to prevent 1 of the outcomes listed above, or involves suspected transmission via a medicinal product of an infectious agent. Examples of such medical events include allergic bronchospasm requiring intensive treatment in an emergency room or at home, blood dyscrasias or convulsions that do not result in inpatient hospitalization, or the development of drug dependency or drug abuse; any organism, virus, or infectious particle (eg, prion protein transmitting Transmissible Spongiform Encephalopathy), pathogenic or nonpathogenic, is considered an infectious agent.

Clarification should be made between a serious AE (SAE) and an AE that is considered severe in intensity (Grade 3 or 4), because the terms serious and severe are NOT synonymous. The general term *severe* is often used to describe the intensity (severity) of a specific event; the event itself, however, may be of relatively minor medical significance (such as a Grade 3 headache). This is NOT the same as *serious*, which is based on patient/event outcome or action criteria described above, and is usually associated with

events that pose a threat to a patient's life or ability to function. A severe AE (Grade 3 or 4) does not necessarily need to be considered serious. For example, a white blood cell count of $1000/\text{mm}^3$ to less than 2000 is considered Grade 3 (severe) but may not be considered serious. Seriousness (not intensity) serves as a guide for defining regulatory reporting obligations.

8.2 Procedures for Reporting Serious Adverse Events

Adverse Events may be spontaneously identified by the patient and/or in response to an open question from study personnel or revealed by observation, physical examination, or other diagnostic procedures. Any clinically relevant deterioration in laboratory assessments or other clinical finding is considered an AE. When possible, signs and symptoms indicating a common underlying pathology should be noted as one comprehensive event. For serious AEs, the investigator must determine both the intensity of the event and the relationship of the event to study drug administration. For serious pretreatment events, the investigator must determine both the intensity of the event and the relationship of the event to study procedures.

Adverse Events which are **serious** must be reported to Millennium Pharmacovigilance (or designee) from the date the participant signs Informed Consent through 30 days after administration of the last dose of ixazomib. Any SAE that occurs at any time after completion of ixazomib treatment or after the designated follow-up period that the sponsor-investigator and/or sub-investigator considers to be related to any study drug must be reported to Millennium Pharmacovigilance (or designee). In addition, new primary malignancies that occur during the follow-up periods must be reported, regardless of causality to study regimen, for a minimum of three years after the last dose of the investigational product, starting from the first dose of study drug. All new cases of primary malignancy must be reported to Millennium Pharmacovigilance (or designee).

Planned hospital admissions or surgical procedures for an illness or disease that existed before the patient was enrolled in the trial are not to be considered AEs unless the condition deteriorated in an unexpected manner during the trial (e.g., surgery was performed earlier or later than planned). All SAEs should be monitored until they are resolved or are clearly determined to be due to a patient's stable or chronic condition or intercurrent illness(es).

Since this is an investigator-initiated study, the principal investigator [name]., also referred to as the sponsor-investigator, is responsible for reporting serious adverse events (SAEs) to any regulatory agency and to the sponsor-investigator's EC or IRB.

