⁹ Clinical assessment (physical exam including performance status, adverse event and clinical disease assessment) will be performed on Day 1 of each cycle (+/-3 days) through the first 8 cycles. After cycle 8, clinical assessments will be performed on Day 1 of each odd-numbered cycle (+/-6 days). For Cycle 1, Day 1, the screening clinical assessment may be used. A Cycle 1, Day 14 (+/-3 days) clinical assessment is strongly recommended.

¹⁰ Labs will be performed on Day 1 (+/-3 days) of each cycle for the first 8 cycles. After cycle 8, labs will be performed on Day 1 (+/-6 days) of each cycle. Labs may be performed at local laboratories with appropriate review by the PI/ Sub-I. For Cycle 1, Day 1, labs performed within 14 days are acceptable. Cycle 1, Day 14 (+/-3 days) labs are strongly recommended.

¹¹ Treatment phase tumor evaluation labs and/or imaging will be performed every 8 weeks of therapy (+/- 6 days) during the first 32 weeks, and approximately every 16 weeks of therapy thereafter, or as indicated per clinical standard of care (e.g. as appropriate for disease, to evaluate clinical suspicion of disease progression).

¹² End-of-treatment evaluations should be done within 30 days of the last dose of ixazomib or prior to the start of a new anti-neoplastic drug, whichever is first. Tumor assessment labs and/or imaging will be performed at end-of-treatment evaluation only for subjects who did not have tumor assessment labs and/or imaging performed within 60 days of end-of-treatment.

Long-term follow-up should be done according to the patient's physicians standard of care. This may be performed at the patient's local physician's offices. Long-term follow-up will assess survival and disease progression; for clarification, subjects may be contacted by the study team until death, withdrawal of consent, lost to follow-up, or study termination by the sponsor-investigator, whichever occurs first.

Table of Contents

PROTOCOL SUMMARY	2
STUDY OVERVIEW DIAGRAM	3
SCHEDULE OF EVENTS.....	4
LIST OF ABBREVIATIONS AND GLOSSARY OF TERMS	8
1. BACKGROUND AND STUDY RATIONALE	12
1.1 Scientific Background	12
1.1.1 Disease Under Treatment	12
1.1.2 Ixazomib	12
1.2 Preclinical Experience	12
1.3 Clinical Experience	12
1.4 Pharmacokinetics and Drug Metabolism	13
1.5 Clinical Trial Experience Using the Oral Formulation of Ixazomib	14
1.6 Relapsed and/or Refractory Multiple Myeloma	20
1.7 Newly Diagnosed Multiple Myeloma (NDMM).....	21
1.9 Study Rationale	21

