Lymphopenia	20 (10)
Skin and subcutaneous tissue disorders	90 (45)
Rash macular ^a	23 (11)
Musculoskeletal and connective tissue disorders	93 (46)
Back pain	24 (12)
Arthralgia	28 (14)
Respiratory, thoracic and mediastinal disorders	78 (39)
Cough	28 (14)
Dyspnea	30 (15)
Infections and infestations	89 (44)
Upper respiratory tract infection	31 (15)

Source: Ixazomib Investigator's Brochure Edition 7

Abbreviations: MedDRA = Medical Dictionary for Regulatory Activities, version 15.0.

Subject Incidence: A subject counts once for each preferred term. Percentages use the number of treated subjects as the denominator.

a Note that rash maculopapular and rash macular represent the 2 most common terms used to describe rash.

Treatment emergent is defined as any AE that occurs after administration of the first dose of any study drug through 30 days after the last dose of any study drug, any event that is considered drug-related regardless of the start date of the event, or any event that is present at baseline but worsens in intensity or is subsequently considered by the investigator to be drug-related.

Subject Incidence: A subject counts once for each preferred term. Percentages use the number of treated subjects as the denominator

Several studies are investigating oral ixazomib in combination with standard combination regimens. The most frequent (at least 10%) AEs occurring in the pooled safety population from Studies C16005, C16006, C16008, and C16013 are shown for all grades (Table 1-3). Note that in combination trials, related is defined as related to any study drug in the combination regimen.

Table 1-3 Most Common (At Least 10% of Total) Treatment-Emergent Adverse Events in Oral Combination Studies

Primary System Organ Class Preferred Term	Total Oral Combo Agent (5/6/8/13) n = 173 n (%)
Subjects with at Least One Adverse Event	163 (94)
Gastrointestinal disorders	139 (80)
Nausea	65 (38)
Diarrhea	81 (47)
Vomiting	51 (29)
Constipation	57 (33)
General disorders and administration site conditions	132 (76)
Fatigue	76 (44)
Pyrexia	39 (23)
Edema peripheral	61 (35)
Asthenia	20 (12)
Nervous system disorders	115 (66)
Headache	28 (16)
Dizziness	34 (20)
Neuropathy peripheral	45 (26)
Metabolism and nutrition disorders	91 (53)
Decreased appetite	25 (14)
Hypokalemia	34 (20)
Blood and lymphatic system disorders	88 (51)
Thrombocytopenia	49 (28)
Anemia	45 (26)
Neutropenia	43 (25)
Lymphopenia	20 (12)
Skin and subcutaneous tissue disorders	102 (59)

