2.2 Secondary Objectives

- To evaluate efficacy parameters including the duration of response (DOR), progression-free survival (PFS), time to next therapy (TNT), and complete response rate (CR) of ixazomib in untreated indolent B-NHL.
- To evaluate the safety and tolerability of ixazomib in subjects with B-NHL.
- To evaluate the safety and tolerability of ixazomib plus rituximab in subjects with B-NHL.
- To evaluate the efficacy parameters including ORR, DOR, TNT, PFS, and CR of the combination of rituximab with ixazomib.

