6.2 Study Drug Administration

Ixazomib Administration

All protocol-specific criteria for administration of study drug must be met and documented before drug administration. Study drug will be administered or dispensed only to eligible patients under the supervision of the investigator or identified sub-investigator(s). Patients should be monitored for toxicity, as necessary, and doses of ixazomib should be modified as needed to accommodate patient tolerance to treatment; this may include symptomatic treatment, dose interruptions, and adjustments of ixazomib dose (see Section 6.2).

Capsules of ixazomib will also be referred to as study drug. Study drug will be supplied by Millennium as capsules of 0.2, 0.5, and 2.0 mg, or as capsules of 2.3, 3.0 and 4.0 mg ixazomib, depending on available ixazomib formulation.

The prescribed administration of ixazomib doses in this study is 4 mg ixazomib q7 days in a q28 day cycle. Sufficient drug will be dispensed for each interval of evaluation at the FHCC, that is, either for 1 or 2 cycles of therapy.

Patients should be instructed to swallow ixazomib capsules whole, with water, and not to break, chew, or open the capsules. Study drug should be taken on an empty stomach (no food or drink) at least 1 hour before or 2 hours after a meal. Each capsule should be swallowed separately with a sip of water. A total of approximately 8 ounces (240 mL) of water should be taken with the capsules.

Missed doses can be taken as soon as the patient remembers if the next scheduled dose is 72 hours or more away. A double dose should not be taken to make up for a missed dose. If the patient vomits after taking a dose, the patient should not repeat the dose but should resume dosing at the time of the next scheduled dose.

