6.3 Administration of Rituximab

Rituximab will be administered at a standard dose of 375 mg/m² by intravenous infusion weekly for 4 consecutive weeks upon completion of the 6-cycle window period of ixazomib monotherapy. Rituximab will be administered per institution standard treatment plan with medications for infusion-reaction prophylaxis and/or treatment given at the discretion of the investigator. Ixazomib will be continued uninterrupted during and after the rituximab therapy. Dose modification or delay to rituximab may be made according to the discretion of the investigator.

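### The SAE reporting window and the closing visits run from the last ixazomib dose only, so part of the 30 days after rituximab is uncovered if ixazomib stops first

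*Combined protocol and SAP*

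**What the plan says.** - **Reporting window (8.2).** SAEs of any cause go to Millennium Pharmacovigilance "from the date the participant signs Informed Consent through 30 days after administration of the last dose of ixazomib".
- **After the window (8.2).** There is an open-ended rule: "Any SAE that occurs at any time after completion of ixazomib treatment or after the designated follow-up period" that the sponsor-investigator or sub-investigator "considers to be related to any study drug must be reported to Millennium Pharmacovigilance (or designee". It applies only to SAEs judged related.
- **Closing visits.** Footnote 12 of the Schedule of Events states: "End-of-treatment evaluations should be done within 30 days of the last dose of ixazomib", or before a new anti-neoplastic drug if that comes first. The Study Completion Assessment in 4.1 sets the same 30 days from the last ixazomib administration.
- **Rituximab (6.3).** It is given "weekly for 4 consecutive weeks upon completion of the 6-cycle window period of ixazomib monotherapy". Ixazomib is meant to carry on through and beyond the course. Rituximab may be delayed at the investigator's discretion, with no stated maximum.
- **Objective (2.2).** "To evaluate the safety and tolerability of ixazomib plus rituximab in subjects with B-NHL".
- **Meaning of study drug.** Section 6.2 says "Capsules of ixazomib will also be referred to as study drug". Section 8.2, on causality, speaks of study drugs in the plural without naming rituximab.
- **Treatment-emergent period.** Section 7.4.5 summarises treatment-emergent AEs without giving the period. The only definition in the document is a footnote to the background Table 1-2, which runs "through 30 days after the last dose of any study drug".

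**The concern.** Two drugs are given on protocol, and the safety of giving them together is an objective, but every end-of-follow-up clock for safety is tied to one of them. Section 6.4 allows ixazomib to be held and then discontinued, and nothing in the protocol says what then happens to rituximab. If a patient's last rituximab infusion comes after the last ixazomib dose, the window can close soon after that infusion, or before it. SAEs then judged unrelated need not be reported to Millennium, and the last scheduled AE assessment may be due too early to see what follows the infusion. All-cause collection matters in a single-arm, investigator-assessed trial because it does not depend on a correct attribution at the time.

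**Working it through.** The plan has no calculated figure to reproduce here; the 30 days is a stated rule. The check is a day count.

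**Inputs**
- 28-day cycles, with ixazomib every 7 days (6.2): cycle days 1, 8, 15 and 22.
- Four weekly rituximab infusions after cycle 6 (6.3): on schedule, cycle 7 days 1, 8, 15 and 22.
- Window end = last ixazomib day + 30 (8.2).
- A delay at the start of a cycle may run to 3 weeks before ixazomib is discontinued, or as the investigator decides (6.4.1).

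**Study days.** Study day = (cycle − 1) × 28 + cycle day.
- Cycle 6 day 15 = 5 × 28 + 15 = 155; cycle 6 day 22 = 162.
- Cycle 7 day 1 = 6 × 28 + 1 = 169; then 176, 183 and 190.

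**Coverage.** Days covered after the last infusion = max(0, min(30, last ixazomib + 30 − last rituximab)). Days lost = 30 − days covered.

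Rituximab on schedule (last infusion day 190):

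| Last ixazomib | Window closes | Covered | Lost |
|---|---|---|---|
| 190 | 220 | 30 | 0 |
| 183 | 213 | 23 | 7 |
| 176 | 206 | 16 | 14 |
| 169 | 199 | 9 | 21 |
| 162 | 192 | 2 | 28 |
| 155 | 185 | 0 | 30 |

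In the last row the window closes before the fourth infusion.

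**Rituximab delay (assumed range, since no maximum is given).** For last ixazomib on day 183, 176, 169 or 162:
- last infusion 7 days late (day 197): 14, 21, 28 or 30 days lost;
- last infusion 14 days late (day 204): 21, 28, 30 or 30 days lost.

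**Thresholds.** Losing more than half of the 30 days needs at least 16 days between the two last doses. Losing all of them needs at least 30.

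**Can it happen?** Cycle 7 day 1 is both a start-of-cycle check for ixazomib (6.4.1) and, on schedule, the first infusion day. A 3-week hold from day 169 ends on day 169 + 21 = 190, the day of the fourth infusion. If ixazomib is then not resumed, its last dose was on day 162 at the latest.

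**What is lost, by type of event, once the window has closed**
- SAE judged related to ixazomib: still reportable, without time limit.
- SAE judged related to rituximab alone: unclear, because 6.2 attaches the term study drug to the capsules while 8.2 uses the plural.
- SAE judged unrelated: no longer reportable under this rule.
- Non-serious AE: end of treatment is the last AE assessment on the calendar, and long-term follow-up covers only survival and progression. The cycle 8 day 1 assessment (day 7 × 28 + 1 = 197) helps only if the patient still counts as in the treatment phase.

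**With the later drug as anchor.** The window would close on day 190 + 30 = 220 in every on-schedule row, so no days are lost. The extension is last rituximab − last ixazomib: 7, 14, 21, 28 or 35 days.

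**The case against.** The strongest reply is that the gap needs a departure from plan. Section 6.3 has ixazomib continuing during and after rituximab, so on plan the window outlasts the course, and no passage expressly provides for rituximab after ixazomib has stopped. That stands, and it makes this a conditional gap. But the protocol's silence also means that nothing prevents it, and 6.4 supplies the trigger.

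Second, the 8.2 window governs reporting to Millennium, not the analysis. Section 7.4.5 sets no 30-day cut-off, 8.2 separately makes the sponsor-investigator responsible for reporting to regulators and the IRB, and survival is followed long term. That also stands. A reader might infer that combination toxicity will be understated, or that the affected patients mostly stopped for toxicity; the documents show neither.

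Third, the open-ended rule keeps related SAEs reportable. This removes a large part of the gap. Rituximab administration also sits in the chapter headed Study Drug, which favours the broad reading of that term, but 6.2 points the other way and the text never settles it.

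Fourth, a reader might infer that most or all of the 30 days is generally lost. It is not. For a stop during an on-schedule course (last dose on day 169, 176 or 183), the loss exceeds half in one case of three and is total in none.

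Finally, the Table 1-2 footnote describes pooled background studies and is not a rule of this trial. It shows a workable wording; it does not create a contradiction.

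**Conclusion.** The point holds as a conditional gap. All three clocks ignore rituximab. If rituximab is the last drug given, 7 to 28 of the 30 days after an on-schedule last infusion fall outside the all-cause SAE window for last ixazomib doses on days 183 to 162, and all 30 once the two last doses are 30 or more days apart. The certain losses are the reporting of SAEs judged unrelated and the timing of the last scheduled AE assessment; SAEs related to rituximab alone are uncertain. This assumes weekly dosing as in 6.2, rituximab starting on cycle 7 day 1, and rituximab continuing after ixazomib stops, which the protocol neither provides for nor rules out. How many patients this concerns cannot be derived from the documents. The correction is worth making because it is cheap and bears on a stated objective; it is not evidence that safety has been misreported.

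**What to change.** 1. In 8.2, footnote 12 and the Study Completion Assessment in 4.1, replace the ixazomib-only anchor with *last dose of ixazomib or rituximab, whichever is later*. Keep the existing footnote 12 clause on starting a new anti-neoplastic drug. All three places must change together, or a new inconsistency arises.
2. State in 8.2 that *any study drug* means ixazomib or rituximab.
3. Use the same end date to define treatment-emergent AEs in 7.4.5.

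If all rituximab courses are already complete, which the documents do not say, the sponsor can identify from dosing records the patients whose last infusion followed their last ixazomib dose, retrieve their events, and fix the treatment-emergent period before reporting combination safety.

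The cost is wording, up to about 4 to 5 more weeks of SAE collection (28 to 35 days in the on-schedule cases above, longer if rituximab is delayed), and a later date for an existing visit. This applies only to patients whose ixazomib stops first. No visit is added, and no dose or treatment rule changes.

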- SAE Report Form (provided by Millennium)

- US FDA MedWatch 3500A
<https://www.fda.gov/downloads/aboutfda/reportsmanualsforms/forms/ucm048334.pdf>
- Any other form deemed appropriate by the sponsor-investigator

8.3 Procedures for Reporting Drug Exposure During Pregnancy and Birth Events

If a woman becomes pregnant or suspects that she is pregnant while participating in this study, she must inform the investigator immediately and permanently discontinue study drug. The sponsor-investigator must immediately fax a completed Pregnancy Form to the Millennium Department of Pharmacovigilance or designee (see Section 8.2). The pregnancy must be followed for the final pregnancy outcome.

If a female partner of a male patient becomes pregnant during the male patient's participation in this study, the sponsor-investigator must also immediately fax a completed Pregnancy Form to the Millennium Department of Pharmacovigilance or designee (see Section 8.2). Every effort should be made to follow the pregnancy for the final pregnancy outcome.

Suggested Pregnancy Reporting Form:
Pregnancy Report Form (provided by Millennium)

9. ADMINISTRATIVE REQUIREMENTS

9.1 Data and Safety Monitoring Plan

Institutional support of trial monitoring will be in accordance with the FHCRC/University of Washington Cancer Consortium Institutional Data and Safety Monitoring Plan. Under the provisions of this plan, FHCRC Clinical Research Support coordinates data and compliance monitoring conducted by consultants, contract research organizations, or FHCRC employees unaffiliated with the conduct of the study. Independent monitoring visits occur at specified intervals determined by the assessed risk level of the study and the findings of previous visits per the institutional DSMP.

In addition, protocols are reviewed at least annually and as needed by the Consortium Data and Safety Monitoring Committee (DSMC), FHCRC Scientific Review Committee (SRC) and the FHCRC/University of Washington Cancer Consortium Institutional Review Board (IRB). The review committees evaluate accrual, adverse events, stopping rules, and adherence to the applicable data and safety monitoring plan for studies actively enrolling or treating patients. The IRB reviews the study progress and safety information to assess continued acceptability of the risk-benefit ratio for human subjects. Approval of committees as applicable is necessary to continue the study.

The trial will comply with the standard guidelines set forth by these regulatory committees and other institutional, state and federal guidelines.

